### 3.2. Secondary Endpoint(s)/Event(s)/Outcome(s):

1. Working memory has been shown to play a role in non-fluent aphasia. Working memory is assessed using the N-back task. Scoring is binary and each response is either scored as correct =1 or incorrect =0 to obtain a raw score that is a scaled variable. We are interested in learning if the working memory score changes after intervention and if the change has a relationship with any changes in language as measured above in the primary endpoint.

*Hypothesis: We hypothesize the working memory score will significantly increase after the real tDCS intervention, but not after the sham intervention. We also hypothesize a significant positive relationship between the working memory score and the scores across all three discourse tasks.*

*These data will be collected at four points in time:*

- 1) Initial baseline;
- 2) Post intervention (A or B);

## MEDICAL PROTOCOL (HRP-590)

PROTOCOL TITLE: Combining cerebellar tDCS and constraint-induced language therapy in non-fluent aphasia: a novel approach to target discourse

VERSION DATE: 08/09/2023

- 3) Follow-up baseline (after washout period);
- 4) Post intervention (A or B)

2. An increase in delta wave percentage during resting state EEG has been shown in individuals with aphasia. The standard practice is to conduct a 2 minute resting state EEG while eyes are open. Data is then processed through EEGLab in MATLAB to “pull out” the amount of delta wave bands/total wave bands to identify a percentage of delta waves within the 2 minute sample. We are interested in learning if this delta percentage changes after intervention and if the change may be associated with any changes in language as measured above in the primary endpoint. The delta wave value is calculated by dividing the number of delta waves present/total waves within the 2 minute sample and represented in a percentage. The delta wave percentage will be calculated for each of the following EEG locations: Fp1, F3, F7 and Fz of the 10/20 International EEG system. This would provide a neurophysiologic rationale for the changes in language.

*Hypothesis: We hypothesize the delta percentage to significantly decrease after the real tDCS intervention, but not after the sham intervention. We also hypothesize a significant negative correlation between the delta percentage and scores across the discourse tasks, with lower delta wave percentage, language scores will be higher.*

These data will be collected at four points in time:

- 1) Initial baseline;
- 2) Post intervention (A or B);
- 3) Follow-up baseline (after washout period);
- 4) Post intervention (A or B)

3. Quality of Life will be assessed using an abbreviated version of the Stroke and Aphasia Quality of Life Scale-39 (SAQOL-39) (Hilari et al., 2003) , which uses a Likert Scale 1-5. Completion of the SS-QOL results in a raw score, which will be a scaled variable. We are interested in the relationship between QOL and changes in language as measured above. *Hypothesis: We hypothesize the raw score of the SAQOL will significantly increase after the real tDCS intervention, but not after the sham intervention. We also hypothesize the score on the SAQOL will be positively and significantly correlated with scores across the discourse tasks.*

These data will be collected at four points in time:

- 1) Initial baseline;
- 2) Post intervention (A or B);
- 3) Follow-up baseline (after washout period);
- 4) Post intervention (A or B)

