### 1. Objectives

#### 1.1. Purpose:

*To determine the effect of combining constraint-induced language therapy (CILT) with cerebellar tDCS in individuals with non-fluent aphasia after stroke.*

*The primary aims are to 1) determine the effect of combining cerebellar tDCS with constraint-induced language therapy (CILT) on language as measured by a verbal fluency task and discourse analysis task in a prospective, crossover study of adults with non-fluent aphasia after a cortical stroke and 2) demonstrate feasibility and data collection to inform a larger study.*

*The secondary aims include impact of the combined intervention on 1) resting state spectral EEG as measured through delta wave percentage 2) working memory as measured by the score on the Wisconsin Card Sorting Test and 3) quality of life as measured by the Stroke Aphasia Quality of Life survey tool. A final secondary aim will be to identify the tolerance of the intervention and barriers to participation measured by the adverse events questionnaire.*

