## MEDICAL PROTOCOL (HRP-590)

PROTOCOL TITLE: Combining cerebellar tDCS and constraint-induced language therapy in non-fluent aphasia: a novel approach to target discourse

VERSION DATE: 08/09/2023

*understanding of the role of the DTC and its potential for neuroplastic change after cortical stroke will be included in the interpretation.*

*Neurophysiologic data from EEG will reveal not only the impact of tDCS on alpha and delta bands but the relationship to discourse. Finally, we will be able to document changes to quality of life and determine if changes are related to the experimental intervention.*

*From an educational perspective, this project will provide a valuable inter-professional experience for graduate students from the Departments of Communication Sciences and Disorders and Department of Computer Science. Such cross-college collaborations are an institutional priority on the University of Minnesota, Duluth campus.*

*This body of work has the potential to lead to the development of a new intervention protocol for non-fluent aphasia and provide the neurophysiologic rationale for the changes observed. Together, this will drive the field of neurorehabilitation forward in creating novel, innovative interventions for optimal functional recovery.*

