## MEDICAL PROTOCOL (HRP-590)

PROTOCOL TITLE: Combining cerebellar tDCS and constraint-induced language therapy in non-fluent aphasia: a novel approach to target discourse

VERSION DATE: 08/09/2023

*associated with expressive language, motor planning and programming and cognition. In fact, the right cerebellum has been shown to play a role in word retrieval and generation, working memory, language learning and semantic processing (Murdoch, 2010; Stoodley, 2012) and diaschesis in the right cerebellum has been shown in chronic non-fluent aphasia (Abe et al., 1997). This, paired with the distance from the stroke lesion site makes the right cerebellum a desirable location for stimulation. The combination of tDCS behavioral language intervention has resulted in improved naming in individuals with aphasia (Sebastian et al., 2017, 2020; Turkeltaub et al., 2016). However, there has been no evidence regarding other functional language skills such as discourse.*

*Finally, another research priority has been the inclusion of neurophysiologic measures in intervention studies to better understand the neural underpinnings of the experimental intervention (Cherney et al., 2008, 2011). Although functional magnetic resonance imaging is the tool most often recommended, it has many contraindication such as cost, availability, and individual comfort and tolerance. Although EEG acquires different data than fMRI, it is a measure of neurophysiology. It is also non-invasive, more accessible and cost-effective, fairly fast to acquire and well-tolerated. Resting state EEG has been identified as a viable tool to investigate electrical brain activity in those with post-stroke aphasia (Dalton et al., 2021) and is sensitive to changes after tDCS (Boonstra et al., 2016). Since an increase in delta frequency bands has been associated with the language deficits observed in aphasia (Hensel et al., 2004; Spironelli & Angrilli, 2009), one would hypothesize it may be a sensitive measure to determine the neurophysiologic impact of a language intervention such as that in the proposed study. In addition, an increased peak alpha frequency has been associated with improved attention and “cognitive preparedness” which would also be an expected outcome of the proposed intervention.*

*This pilot study has the potential to inform a larger, externally funded clinical trial that may lead to an innovative, novel approach to improve functional language in those with non-fluent aphasia.*

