## MEDICAL PROTOCOL (HRP-590)

PROTOCOL TITLE: Combining cerebellar tDCS and constraint-induced language therapy in non-fluent aphasia: a novel approach to target discourse

VERSION DATE: 08/09/2023

*open-ended questions regarding barriers to participation will be analyzed to identify common themes.*

- Primary outcome measures, main concept discourse scores and verbal fluency counts, will be compared between treatment conditions using mixed effects generalized linear models, with fixed effects for treatment, period, sequence, pre-post time point, and treatment by pre-post time point interaction, and random effects for participant within sequence. This will provide difference-in-differences (post-treatment minus pre-treatment) estimates for the treatment effect which will be reported along with 95% confidence intervals as a measure of precision. Similar models will be used to analyze the secondary outcome measures including WI card sorting task, EEG delta wave, and SAQOLL.*
- Estimates from these models will provide important information for planning a well-powered clinical trial that are not obtainable elsewhere. Estimates that will be gathered in this pilot trial that will inform the subsequent power calculation include the treatment effect size, within-participant correlation of repeated measures, and random effects variance, for each of the outcome measures.*
- Pearson's Correlation will be conducted to determine the relationship between primary outcome variables (discourse and working memory scores) and SS-QOL as well as other scaled demographic variables such as age and duration since stroke.*
- Spearman's Rho Correlation analyses will be conducted to determine the relationships between primary outcome variables (discourse and working memory) and EEG data, reported in percentage.*
- The multivariate repeated measures and correlation analyses may not be terribly informative as the pilot sample size may lack the power for these statistics. However, they may be useful in descriptive interpretation of the data and lay the foundation for the larger clinical trial.*

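### The only explicit formula for the EEG delta endpoint is a ratio of wave counts, which can fall with delta unchanged when faster rhythms speed up

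*Combined protocol and SAP*

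**What the plan says.** The protocol describes the EEG endpoint in three ways.

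- Section 1.1 names the secondary aim as "resting state spectral EEG as measured through delta wave percentage". It gives no formula.
- Section 3.2, item 2, first describes extracting "the amount of delta wave bands/total wave bands to identify a percentage of delta waves within the 2 minute sample". It does not say whether the amount is a count, a duration or a power.
- The same item then gives the calculation: "The delta wave value is calculated by dividing the number of delta waves present/total waves within the 2 minute sample". The result is a percentage, computed separately at Fp1, F3, F7 and Fz.

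No section gives band limits, a rule for detecting a wave, or an absolute measure of delta.

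The hypothesis in Section 3.2 is: "We hypothesize the delta percentage to significantly decrease after the real tDCS intervention, but not after the sham intervention". Section 15.3 applies to the secondary outcomes a model like the primary one, which yields "difference-in-differences (post-treatment minus pre-treatment) estimates for the treatment effect". It also plans Spearman correlations of the EEG data with discourse and working memory.

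On alpha, Section 2.1 says the EEG will show "the impact of tDCS on alpha and delta bands but the relationship to discourse". Section 2.3 says that "an increased peak alpha frequency has been associated with improved attention and “cognitive preparedness” which would also be an expected outcome of the proposed intervention".

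**The concern.** A count ratio gives every wave the same weight. A 2 Hz delta wave lasting 0.5 s counts the same as a 10 Hz alpha wave lasting 0.1 s. When alpha speeds up, more alpha waves fit into the 2 minutes, the denominator grows and the delta percentage drops. Nothing need have happened to delta.

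That drop is in the hypothesised direction. If the alpha change follows real stimulation and not sham, neither the sham comparison nor the crossover removes it, and the difference-in-differences estimate reports it as a treatment effect on delta. Only a shift of similar size under both conditions would largely cancel. The planned correlations would carry the same ambiguity, because a lower percentage could mean less delta or faster alpha.

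Section 3.2 wants this endpoint to explain language change in neurophysiologic terms, and Section 15.3 wants its effect size and variance for planning the larger trial. A measure that cannot separate the two explanations serves neither purpose well.

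**Working it through.** The documents state no numerical value for this endpoint, so there is no plan figure to reproduce. The check evaluates the stated formula.

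**Inputs from the documents:** the count formula and the 2-minute (120 s) sample, both in Section 3.2.

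**Assumed inputs (not in the documents):** delta at 2 or 3 Hz (1-3 Hz in one grid), theta 6 Hz, beta 20 Hz, alpha starting at 9 Hz and moving to 10 or 11 Hz, and the share of time taken by each rhythm.

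**Direction.** Let D, A and O be the counts of delta, alpha and other waves, so R = D/(D + A + O). With alpha present for T_A seconds at frequency f, A = T_A × f. Holding D and O fixed, dR/df = −D × T_A/(D + A + O)², which is negative whenever delta and alpha are both present. The relative fall is 1 − (old total)/(new total).

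**Delta and alpha only, taking turns, alpha 9 to 11 Hz:**

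| Delta time share, frequency | R at 9 Hz | R at 11 Hz | Relative fall |
|---|---|---|---|
| 50%, 2 Hz | 120/(120+540) = 18.2% | 120/(120+660) = 15.4% | 15.4% |
| 50%, 3 Hz | 180/(180+540) = 25.0% | 180/(180+660) = 21.4% | 14.3% |
| 30%, 2 Hz | 72/(72+756) = 8.7% | 72/(72+924) = 7.2% | 16.9% |
| 30%, 3 Hz | 108/(108+756) = 12.5% | 108/(108+924) = 10.5% | 16.3% |

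For a 1 Hz shift (9 to 10 Hz) in this two-rhythm model, with delta shares of 20-60% and delta at 1-3 Hz, the relative fall is 6.9% to 9.8%. For example, with delta at 2 Hz for 40% of the time, R goes from 12.90% to 11.76%.

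**Theta and beta also counted, alpha 9 to 10 Hz, delta 2 Hz:**

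| Time shares: delta, theta, alpha, beta | R at 9 Hz | R at 10 Hz | Relative fall |
|---|---|---|---|
| 40, 20, 30, 10% | 96/804 = 11.94% | 96/840 = 11.43% | 4.3% |
| 25, 25, 25, 25% | 60/1110 = 5.41% | 60/1140 = 5.26% | 2.6% |
| 40, 25, 10, 25% | 96/984 = 9.76% | 96/996 = 9.64% | 1.2% |

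**Four bands, alpha 9 to 11 Hz, delta 2 Hz.** With all rhythms present throughout, the counts are 240 + 720 + 1080 + 2400 = 4440, rising to 4680. R goes from 5.41% to 5.13%, a relative fall of about 5%. With an alpha-heavy split (20, 10, 60, 10%), the total goes from 1008 to 1152. R goes from 48/1008 = 4.76% to 48/1152 = 4.17%, a relative fall of 12.5%.

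**Power instead of counts.** A synthetic 120 s signal had identical delta (240 waves) and alpha moved from 9 to 10 Hz at constant amplitude. The count ratio fell from 5.41% to 5.26%, while relative delta power stayed at 53.33%.

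**Limit of relative power.** Start with delta and alpha power equal, so relative delta power is 50.0%. A 10% rise in alpha amplitude multiplies alpha power by 1.1² = 1.21, and relative delta power becomes 1/(1 + 1.21) = 45.2% with delta unchanged.

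**The case against.** The strongest reply is that the count formula is loose wording. Section 1.1 says spectral, Section 3.2 speaks of bands and names EEGLab, and without a wave-detection rule the count cannot be run as written. The sponsor may have meant band power, and a pure alpha frequency shift would then have no effect. It is fair that the documents do not establish that counts will in fact be used. But neither of the other phrases defines a measure, and the count is the only formula an analyst is given. If power was meant, the text misstates the endpoint and still needs correcting.

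A reader might infer that the protocol predicts faster alpha. Section 2.3 does not clearly say so: its expected outcome may be attention and preparedness, with peak alpha only as a correlate. Section 3.2 has no alpha endpoint, hypothesis or size in Hz. The documents support a link to an expected outcome, which is enough to make the mechanism relevant.

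A reader might also take 14-17% as the expected distortion. It needs two rhythms only and a 2 Hz shift, neither of which is in the documents, whereas the stated denominator is all waves. With theta and beta counted, the fall is smaller in every case shown.

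It might further be inferred that relative power alone solves the problem. The 50.0% to 45.2% example shows that it does not.

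Finally, this is a secondary outcome in a pilot aiming for 3 completers (Section 10.1), and Section 15.3 itself concedes that its repeated-measures and correlation analyses may tell little. That limits the stakes, but the measure should still be sound, because its estimates are meant to inform the next trial.

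**Conclusion.** The point holds as a fault in the endpoint's definition. The one stated formula disagrees with the spectral aim and with the wording beside it. Applied as written, it can produce the hypothesised fall with no change in delta.

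The direction follows from arithmetic and rests on no assumption beyond alpha speeding up with the other counts fixed. The size rests wholly on assumed frequencies, time shares and a 1 to 2 Hz shift. Within those, the relative fall runs from about 1-4% to 14-17%, and it may be small if fast waves dominate the count. The documents do not show that alpha will speed up or that any such shift would be confined to real stimulation. This should be corrected, in proportion to a secondary pilot endpoint.

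**What to change.** In Section 3.2, item 2, replace the count formula with band power from the EEGLab spectrum, and bring Section 1.1 and the looser band wording into line with it.

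- Compute it at each of Fp1, F3, F7 and Fz, keeping the per-location plan. Nothing in the documents argues for averaging the sites.
- State the delta limits and the total range (for example 1-4 Hz over 1-30 Hz).
- Report relative delta power together with log absolute delta power. State in advance that a change is attributed to delta only if absolute delta power also falls.
- Report peak alpha frequency as a separate exploratory value.

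In the same edit, say how the three 2-minute recordings in Section 5.2 become the single 2-minute sample of Section 3.2.

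The cost is a protocol wording change and a few lines of script. The same recordings serve, so no visit or procedure is added.

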## MEDICAL PROTOCOL (HRP-590)

PROTOCOL TITLE: Combining cerebellar tDCS and constraint-induced language therapy in non-fluent aphasia: a novel approach to target discourse

VERSION DATE: 08/09/2023

4. An adverse events/experiential survey will be given to participants to provide using a Likert Scale 1-4. In addition two open ended questions will be asked about positive experiences and negative experiences to help us identify barriers to participation. The objective portion will provide us a raw score and the open ended questions will be analyzed qualitatively for agreement and themes. This information will be used to hone the methodology to improve retention and reduce attrition in a larger clinical trial. This survey will be provided at the end of the experience. If a participant drops out, the research team will reach out to ask the participant to complete the survey to assist us in establishing better methodology.

### 4. Study Intervention(s)/Investigational Agent(s)

#### 4.1. Description:

There will be two intervention conditions in this study:

- 1) anodal tDCS (2mA) to the right cerebellum; and
- 2) sham tDCS to the right cerebellum.

The participants will receive 20 minutes of tDCS (sham or real) during constraint-induced language therapy (CILT) followed by an additional 20 minutes of CILT alone.

tDCS (TCT Research Limited; Hong Kong): 5x5 saline-soaked sponge electrodes will be used with the anode placed over the right cerebellar hemisphere; 1cm under and 4cm lateral of the inion targeting lobule VII and the anode will be placed on the right shoulder (Ferrucci et al., 2015; Sebastian et al., 2020). The electrode placement will be the same across both conditions.

CILT: The CILT behavioral intervention will be led by a certified, licensed speech-language pathologist and a graduate student assistant and will follow the guidelines of CILT (Maher et al., 2006; Mozeiko et al., 2016; Pulvermuller et al., 2001). During the behavioral language intervention, participants will engage in language activities such as card games that require verbal expression. Other forms of communication such as gestures and writing will be discouraged and only verbal output will be encouraged through the use of cues and, when needed, models.

As this is a within subject study, all participants will experience both intervention conditions through a cross over design. Each condition will

## MEDICAL PROTOCOL (HRP-590)

PROTOCOL TITLE: Combining cerebellar tDCS and constraint-induced language therapy in non-fluent aphasia: a novel approach to target discourse

VERSION DATE: 08/09/2023

involve 12 intervention sessions across 4 weeks; 3 sessions/week with a 4-week washout period between conditions.

We believe this study meets the criteria for NSR-IDE because (1) Is not an implant and does not present a potential for serious risk to the health, safety, or welfare of a subject; (2) Is not purported and will not be represented to be for use supporting or sustaining human life and presents a potential for serious risk to the health, safety, or welfare of a subject; (3) Will not be used of substantial importance in diagnosing, curing, mitigating, or treating disease, or otherwise preventing impairment of human health and does not present a potential for serious risk to the health, safety, or welfare of a subject; and/or (4) Does not otherwise pose a potential for serious risk to the health, safety, or welfare of a subject.

The sponsor-investigator agrees to comply with the abbreviated IDE requirements in 21 CFR 812.2(b)

4.2. Drug/Device Handling: N/A

4.3. Biosafety: N/A

4.4. Stem Cells: N/A

4.5. Fetal Tissue: N/A

## 5. Procedures Involved

5.1. Study Design:

*Within subject, crossover prospective pilot study.*

5.2. Study Procedures:

*Potential participants will be recruited through the Robert F. Pierce (RFP) Speech-Language and Hearing Clinic on the UMD campus and surrounding communities including stroke support groups and public advertisements using paper and digital flyers. Digital flyers will also be used as posts to the Neural Function and Recovery Lab research lab social media page(s) and the lab website. Past and current clients of the RFP Speech-Language and Hearing Clinic, with a diagnosis of non-fluent aphasia, will be sent a paper flyer in the mail and will be informed of the study by their current graduate student clinician. In addition, paper flyers will be posted in the lobby of the Robert F. Pierce Speech-Language and Hearing Clinic.*

## MEDICAL PROTOCOL (HRP-590)

PROTOCOL TITLE: Combining cerebellar tDCS and constraint-induced language therapy in non-fluent aphasia: a novel approach to target discourse

VERSION DATE: 08/09/2023

*Participants will be screened for eligibility using the screening form (in supplementary documents) to ensure they meet the eligibility requirements. Screening can be done in person or via phone. The individual must provide documentation of a left hemisphere stroke in the form of a physician or clinician report and diagnosis of non-fluent aphasia in the form of a physician or clinical report. If they do not have documentation of their stroke, we will obtain consent from the interested participant to request the medical report. If they do not have documentation of their aphasia diagnosis and are still interested in participating, we will either obtain a consent from the interested participant to request the SLP assessment report or the research team will administer the Western Aphasia Battery Assessment to determine the type and severity of aphasia. Once deemed eligible, a member of the research team will go over the consent form with the individual in person and answer any questions the individual has. Both the participant and research team member will sign the consent form to certify it and a copy will be provided to the participant. Paper copies will then be scanned and stored in Advarra EDC. If the participant is screened through a phone meeting or via virtual visit on Zoom, the consent form will be discussed and shared with the participant through email. Upon coming in for the first baseline assessment visit, the consent form will then be signed.*

*Part of the consent requires participants to not engage in other speech-language therapy sessions outside of those provided in the study. For example, an individual who is currently receiving speech-language therapy services at the RFP Clinic who consents and is enrolled in this study would then only receive the intervention visits outlined in this study for the duration of their enrollment of the study and would then resume speech-language therapy services at RFP Clinic once their participation ends.*

*Careful consideration will be given to those who receive insurance benefits that cover speech-language therapy services at other clinics to ensure a participant won't "lose" insurance coverage for stepping away from traditional speech-language therapy sessions for a 2-month time span. This is typically only an issue for individuals receiving benefits from Medicare A. The PI will talk with potential participants regarding this issue.*

*Participants will attend 17 visits over the course of 2 months, including one visit for screening and consenting process. The screening and consenting visit is expected to last ~30 minutes. If formal testing is needed for the aphasia diagnosis to be confirmed, the screening and consenting visit will last ~90 minutes. Each assessment/data collection visit is expected to last 60-75 minutes. Intervention visits are expected to last 60 minutes for total*

